3.4 Phase III

This phase will include 25 evaluable subjects from Phase I and/or II if they are interested in continued participation. If subjects from Phase I and/or II decline or are no longer eligible, additional subjects may be consented and screened for recruitment utilizing the screening requirements from Phase 1 (Appendix A, Study Calendar 1). Design for testing as described in Phase II to include: simulated workplace protection factor, test chamber, and subject monitoring will be used once more in this phase, minus flow rate adjustments.

This phase includes alteration of the exercise regimen used in Phase I & II by number of exercises, order of exercises, and length of time per exercise to determine Work Rate Effect on individual exercise and overall regimens SWPF values. For this phase, two sets of 3-exercise regimes will be used (Table 6), representing low, moderate, and hard expected work rates, with each exercise taking approximately five minutes. The flow rates in this phase will be constant at the NIOSH minimum for certification (170 L/min for loose-fitting and 115 L/min for tight-fitting).

Two 15-minute regimens (Table 6.) were selected from the exercise regimen in Phase I and II (Table 3.). A ten-minute break for subjects will occur between each regimen in this phase but not in between each exercise within a regimen. Exercise regimens were designed to simulate light, moderate, and hard healthcare activity work rates as determined in Phase I.

25 subjects x 8 PAPR models set at 1 NIOSH minimum approved flow rate x 3 work rates x 3 replicates = 1200 overall SWPF values (based on 2-exercise regimens). Three Way Repeated Measures ANOVA will be used to analyze the data.

Each subject will come in to test 4 PAPRs and 3 work rates (30 min) per visit for an approximate 3 hour test session, meaning subjects will complete the first replicate in 2 visits (~6 hours total). The subjects will repeat this procedure for the second replicate for a total of 4 visits (~12 hours total) to complete Phase III. It is estimated that this phase will take 3-6 months (April 2020-September 2020).

Test subjects wearing the PAPRs will enter the chamber and perform two different exercise regimens (Table 6.). SWPF testing and chamber set up will be the same as during Phase II (Section 3.3). Laser photometer and Dustrak will be used to measure aerosol concentration inside and outside of the respirator, respectively. The SWPF for all particle sizes (10–1,000 nm) inside and outside the respirator will be determined. Each subject will be asked to complete the comfort survey after each PAPR tested in Phase III (Appendix N).

Table 6. Phase III Exercise Regimens

Exercise regime	Exercise #	Test exercise	Approximate Duration (min)	Hypothesized Work Rate
A	2	Reading: read the rainbow passage while standing	5	Light
	6	Reaching up and stepping out (Modified jumping jack): bending the left knee slightly while reaching up both arms overhead & looking up and stepping the right leg out to the side, then repeat with the other leg, at a rate of 10-12 sets/min.	5	Moderate
	9	Perform CPR/AED: perform CPR on a training manikin by compressing chest cavity ~1.5 - 2	5	Hard

		inches at a rate of 80-100 compressions/min. 2 minutes of CPR followed by 1 min AED, followed by 2 more minutes of CPR							
Minimum of 10 minute break in between regimens and vital signs return to within baseline limits									
В	3	Moving head side-to-side: moving head side-to-side at approximately 10 times/min while standing	5	Light					
	7	Walk on a treadmill: walking upright on a treadmill at a speed of 3 mile/h without movement of the head, and without speech.	5	Moderate					
	10	Stair climbing: Stair climbing (using a 3-step ladder) climb rate ~ 10-12 cycles/min (one cycle = up 3 steps and back down 3 steps).	5	Hard					

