- 3) A test operator will: a) turning the blower on, b) adjust/verify the PAPR flow rate, and c) assist the subject with donning each PAPR model using the manufacturer's directions.
- 4) During Phase II only, the PAPR flow rate first to be tested will be the fixed manufacture
- 5) A fingertip-pulse oximeter will be worn by each subject in order to obtain oxygen saturation information. When wearing the PAPR, the test subjects will be instructed on how to communicate with the test operator whenever they feel unable to continue. The tests will be terminated immediately if a subject or investigator notes any potential adverse events or safety parameters reached (Section 7)
- 6) Once the corn oil aerosol concentration in the chamber reaches approximately 20-40 mg/m, the subject will enter the chamber wearing the PAPR model assigned with the blower running. The test operator will connect: 1) a pressure line and 2) all sample lines to particle detector systems. Dustrak and Laser photometer will be used to measure simultaneously to measure the upstream (outside the PAPR) and downstream (inside the PAPR) test aerosol (Fig. 4A & Fig. 4B).
 - 7) After connecting all sample lines, the subject will perform either the 10-exercise regimen shown in Table 3 (Section 3.3), or one of the three 2-exercise regimes in Table 6 (Section 3.4) dependent on the Phase they are enrolled into. Data from the Dustrak and Laser photometer will be recorded and each individual exercise SWPF will be calculated as a ratio of the upstream and downstream particle concentrations.

8) After completing testing with a PAPR and specified flow rate, the subject will exit the test chamber and remove the PAPR. Subjects resting vital signs must return to near baseline and a minimum of a ten-minute break must be provided to the subject between each exercise regimen test if multiple scheduled in one day.

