8.2 Phase II Statistical Methods

For Phase II SWPF values will be calculated as the ratio of time-weighted average C_{out}/C_{in} for the summation particles across the size range measured, for each exercise. Overall SWPF for each attempt of a subject wearing each respirator model will be determined by taking the harmonic mean of the SWPF for all individual SWPF exercises. The performance of the respirators across the size range measured will be determined using the 5th percentile and geometric mean (GM) SWPF values. The 5th percentile SWPF value will be calculated from the formula GM/GSD^{1.645}, where GSD is geometric standard deviation. A log transformation of the data will be done to adjust for a skewed distribution and extreme outliers as described previously (OSHA 2006). For Phase II, a normality test will be conducted for the log transformed dependent variable (i.e. SWPF value for each test) first. If the normality holds, a three-way repeated measures ANOVA will be performed with subject number, respirator model, and work rate/exercise regime and flow rate of the respirator as independent variables, otherwise a Generalized Estimating Equation (GEE) model will be fit using the same set of independent variables. A full factorial design, which includes the main effects of work rate and flow rate, and their interaction, will be used. In this study phase, the data will be analyzed after all 25 subjects complete the first of three replicates with each PAPR and all three flow rates to estimate statistical effects and conduct a power analysis.

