8.3 Phase III Statistical Methods

For Phase III, the same analysis approach as in Phase II will be used to test the effect of work rate, except excluding the effect of flow rate, since all the PAPRs will be set at the NIOSH minimum approved flow rate. In this study phase, the data will be analyzed after all 25 subjects complete the first of three replicates with each PAPR to estimate statistical effects and conduct a power analysis.

1333	REFERENCES
1334	
1335	American College of Sports Medicine (2013). ACSM's guidelines for exercise testing and prescription,
1336	Lippincott Williams & Wilkins.
1337	
1338	American National Standards Institute (ANSI): ANSI Z88.10-2010, Respiratory Fit Testing Methods,
1339	American Industrial Hygiene Association, Fairfax, VA: ANSI, 2010.
1340	
1341	Bolsover, J. B. Ranan-Sithamparanadarajah and N. Vaughan: Workplace protection of air-fed visors
1342	used in paint-spraying operations. Ann. Occup. Hyg. 50(3): 219-229, 2006.
1343	
1344	Borg G.: Psychophysical scaling with applications in physical work and the perception of exertion.
1345	Scand J Work Environ Health, 16 (Suppl 1):55-58, 1990.
1346	
1347	British Standards Institution (BSI) (a): BSEN 12942:1998+A2:2008. Power assisted filtering devices
1348	incorporating full face masks, half masks or quarter masks. Requirements, testing, marking. London:
1349	British Standards Institution.
1350	
1351	British Standards Institution (BSI) (b): BSEN 12941:1998+A2:2008. Respiratory protective devices:
1352	Respiratory protective devices – Powered filtering devices incorporating a helmet or a hood –
1353	Requirements, testing, marking. London: British Standards Institution.
1354	
1355	Centers for Disease Control and Prevention (2018). OSHA-NIOSH Heat Safety Tool App (3.1.1).
1356	
1357	Clayton, M.P., A.E. Bailey, N.P. Vaughan and R. Rajan: Performance of power assisted respirators
1358	during simulated asbestos removal. Ann. Occup. Hyg. 46(1): 49-59, 2002.
1359	
1360	Cohen, H.J., L.H. Hecker, D.K. Matthies, J.S. Johnson, A.H. Bierman and K.L. Foote: Simulated
1361	workplace protection factor study of powered air-purifying and supplied air respirators AIHAJ
1362	62(5):595-604, 2001.
1363	
1364	Da Roza, R.A., C.A. Cadena-Fix and J.E. Kramer: Powered air-purifying respirator study. J. Int. Soc.
1365	Respir. Prot. 8(2): 15-36, 1990.
1366	
1367	Federal Register (2006). Occupational Safety and Health Administration (OSHA). Assigned Protection

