Model 3: Exercise Regimen A & B (Table 6) - Replicate 2	Model 7: Exercise Regimen A & B (Table 6) - Replicate 2
Phase III Survey	Phase III Survey
Model 4: Exercise Regimen A & B (Table 6) - Replicate 2	Model 8: Exercise Regimen A & B (Table 6) - Replicate 2
Phase III Survey	Phase III Survey
NPPTL Post Visit Medical Evaluation ⁵	NPPTL Post Visit Medical Evaluation ⁵

¹Subjects that participated in Phase I must complete consent and screening for Phase II prior to registration if it has been more than a year since their Phase I registration. Rescreening may also be completed within one year, if changes to subject's health and body measurements noted during a study visit (see section 3.1).

² Women of child bearing potential are required to complete a pregnancy test prior to each visit study interventions, which will be reviewed by a U.S. licensed health professional. Only one pregnancy test per 7 calendar days is required and study visits within the same 7 calendar days may waive additional pregnancy tests after first visit in that 7-day period.

³Prior to beginning study interventions at each study visit, subjects and a U.S. licensed health professional must complete the Pre Visit Medical Evaluation form (Appendix L)

⁴Subjects will complete exercise regimens A & B for 4 PAPR models per visit (~3 hours), for a total of four 30-min tests. After the subject completes exercise regimen A, they must receive a minimum of a ten-minute break and vitals must be assessed and have returned to baseline prior to initiating Exercise Regimen B. Subjects must also be provided a minimum of a ten-minute break and vitals must be assessed and have returned to baseline prior to initiating the next models exercise regimen A & B test. Additionally a Phase III Survey (Appendix N) must be completed by the subject at the end of each model tested (four per visit).

⁵Subjects must be given a minimum of a ten-minute break before post visit medical evaluation completed and a U.S. licensed health professional must review their pre and post test medical evaluations (Appendices M & P) before they are dismissed from the visit.

Volunteers Needed in Research Study

Superior Powered Air-purifying Respirator Tests and New Technologies (SPARTAN)

Powered Air-purifying Respirator

study volunteers to participate in research to help improve respirators for use by healthcare workers. This study will be conducted by the National Personal Protective Technology Laboratory (NPPTL) at NIOSH.

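### SWPF per test, the stated dependent variable, cannot carry the work-rate effect of primary objective (b), and the Phase III count of 1,200 contradicts its own factors

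*Protocol*

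**What the plan says.** - **Objective.** Section 2.1(b) makes the relation between work rate and SWPF a primary objective. Phase III is the phase built for it.
- **Regimens.** Section 3.4 says "two sets of 3-exercise regimes will be used (Table 6), representing low, moderate, and hard expected work rates". In Table 6, regimen A is exercises 2, 6 and 9 and regimen B is exercises 3, 7 and 10. Each holds one light, one moderate and one hard exercise.
- **Outcome.** Section 3.3 defines overall SWPF as the harmonic mean of the exercise SWPFs in a test, and section 8.2 repeats this. Section 8.2 names the outcome as the "log transformed dependent variable (i.e. SWPF value for each test". Section 3.3 likewise uses the log SWPF of each test, with work rate as a factor.
- **Model.** Section 8.2 asks for main effects of work rate and flow rate and their interaction. Section 8.3 says "the same analysis approach as in Phase II will be used to test the effect of work rate", leaving out flow rate.
- **Count.** Section 3.4 begins "25 subjects x 8 PAPR models set at 1 NIOSH minimum approved flow rate" and continues "x 3 work rates x 3 replicates = 1200 overall SWPF values (based on 2-exercise regimens".
- **Other figures.** Section 5.3 step 7 speaks of "one of the three 2-exercise regimes in Table 6". Section 8.2 plans an analysis once subjects "complete the first of three replicates with each PAPR and all three flow rates", and section 8.3 also has three replicates. Yet section 3.3 sets two flow rates and two replicates for Phase II, although its comfort-survey sentence mentions three flow rates. The Phase III visit plan in section 3.4 and the Appendix A calendar have two replicates.
- **Exercise-level values.** Section 3.4 gives the aim of Phase III as the work-rate effect on single-exercise SWPF as well as on whole regimens. Sections 5.3 and 8.2 calculate an SWPF for every exercise.

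**The concern.** A factor can be tested only if it differs between observations. Taken as written, each observation is one SWPF per test, already averaged over all the work rates in that test. In Phase III the only remaining contrast is regimen A against regimen B, which compares two sets of tasks with the same mix of work rates. In Phase II every test contains all ten exercises of Table 3, so the work-rate main effect and the work rate by flow rate interaction have nothing to rest on.

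At stake is the stated test of a primary objective. An analyst who follows section 8 literally would either be unable to fit the term or would report the A-versus-B comparison as a work-rate effect. The count in section 3.4 does not help, because it refers to overall values, has a product that does not follow from its factors, and describes regimens that Table 6 does not contain.

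**Working it through.** **1. The printed count.** Inputs from section 3.4: 25 subjects, 8 models, 1 flow rate, 3 work rates, 3 replicates.

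25 × 8 × 1 × 3 × 3 = 1,800. The stated 1,200 is not reproduced.

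**2. What the design gives under each unit of analysis.**

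| Unit of analysis | Product | Values | Does work rate vary between values? |
|---|---|---|---|
| Overall value per regimen, 2 replicates | 25 × 8 × 2 × 2 | 800 | No |
| Overall value per regimen, 3 replicates | 25 × 8 × 2 × 3 | 1,200 | No |
| One value per work rate, 2 replicates | 25 × 8 × 3 × 2 | 1,200 | Yes |
| One value per exercise, 2 replicates | 25 × 8 × 6 × 2 | 2,400 | Yes, 800 per level |
| One value per exercise, 3 replicates | 25 × 8 × 6 × 3 | 3,600 | Yes |

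Two different designs give 1,200. Only one of them has values specific to a work rate.

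**3. Whether work rate varies between overall values.** Write S with the exercise number for each exercise SWPF.

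- Overall A = 3 / (1/S2 + 1/S6 + 1/S9)
- Overall B = 3 / (1/S3 + 1/S7 + 1/S10)

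Each has one light, one moderate and one hard term. Work rate therefore has a single level across these values and 1 − 1 = 0 degrees of freedom. In Phase II its interaction with the two flow rates has (1 − 1) × (2 − 1) = 0.

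**4. Illustration.** The documents give no exercise SWPFs, so these are assumed: light 10,000, moderate 5,000 and hard 1,000 in both regimens.

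3 / (1/10,000 + 1/5,000 + 1/1,000) = 3 / 0.0013 = 2,308 for A and for B.

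The A-to-B ratio is 1 despite a 10-fold difference between light and hard. The choice of figures does not matter: for any light, moderate and hard values common to A and B the ratio is 1, whether the work-rate effect is large or absent. If exercises of the same work rate differ, A and B will differ too, but that difference reflects the tasks and not work rate.

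**5. A wider reading of a test.** Note 4 to the Phase III calendar in Appendix A counts regimens A and B on four models as "for a total of four 30-min tests", so a test there is A plus B. One overall value per test then gives 25 × 8 × 2 = 400 values, and even the A-versus-B comparison is gone.

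**6. The exercise-level data.** Within each subject, model and replicate there are two SWPFs at each work rate: exercises 2 and 3 (light), 6 and 7 (moderate), 9 and 10 (hard). The work-rate contrast is estimable from these within subject and model.

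**The case against.** The best defence is that the plan means exercise-level values. Section 3.4 names them as a target, sections 5.3 and 8.2 calculate them, and the protocol does not define a test. The section 8.2 model, with its work rate by flow rate interaction, can be fitted only to exercise-level values, so a sympathetic analyst would use them. Moreover, Table 6 holds exactly two exercises per work rate. Pairing them gives a 2-exercise value for each of three work rates, and 25 × 8 × 3 × 2 = 1,200 then matches the printed total and the calendar, leaving only the three replicates as a slip.

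Much of this stands. A reader might infer that Phase III cannot estimate the work-rate effect at all. The documents do not support that, because the necessary data are collected. A reader might also infer that 1,200 is left over from a superseded design of three 2-exercise regimens, which section 5.3 seems to echo. No amendment history is shown, and 1,200 arises in more than one way, so this remains a guess. Section 3.3 gives Phase II the purpose of testing flow rate, for which overall SWPF is a sound outcome, so objective (a) is not affected. The illustration in step 4 is true by construction: it shows what the A-versus-B comparison measures, not that the trial would miss an effect.

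The defence does not remove the conflict. Sections 3.3 and 8.2 both put the outcome at the level of the test, and section 3.4 counts overall values. No section describes pairing exercises by work rate, and section 5.3 refers to three regimens that Table 6 does not have. Nor is this a detail left to the statistical analysis plan, because the protocol itself fixes the dependent variable and the factors, and they do not fit together.

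**Conclusion.** The point holds for the dependent variable as stated. With log SWPF per test, the work-rate effect of primary objective (b) and the Phase II work rate by flow rate interaction have zero degrees of freedom. Overall values support only a comparison of regimen A with regimen B. The count is wrong as printed (1,800 from its factors, against 1,200), and its three replicates and 2-exercise regimens conflict with Table 6 and the two-replicate calendar.

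The conclusion rests on reading the SWPF of a test as the harmonic mean over that test's exercises, as sections 3.3 and 8.2 define it. If the sponsor meant exercise-level or work-rate-level values, the fault lies in the wording. The wording still needs correcting before Phase III is analysed, because it specifies the test of a primary objective.

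**What to change.** - In sections 3.3, 3.4, 8.2 and 8.3, state that work-rate effects, and the work rate by flow rate interaction in Phase II, are analysed on log SWPF at exercise level with work rate as a within-subject factor. For Phase III, the harmonic mean of the two same-work-rate exercises is an acceptable alternative. Keep overall SWPF for the flow-rate effect.
- Restate the Phase III count for the chosen unit. With two replicates it is 2,400 exercise-level values, or 1,200 work-rate-level values; regimen-level overall values number 800.
- Reconcile the numbers of regimens, exercises per regimen, replicates and flow rates across sections 3.3, 3.4, 5.3 step 7, 8.2, 8.3 and the Appendix A Phase III calendar.

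The random-effects structure can be left to the statistical analysis plan. The cost is protocol wording only: exercise SWPFs are already recorded, so no extra visit, test or subject is needed.

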Clayton et al. (2002) measured SWPF laboratory performance of two full facepiece PAPRs approved under European performance criteria (BSI, 1992). Limitations included failure to fit test the subjects, protrusion of spectacle temple bars through the face seal, and simulated battery failures, and lack of work rate or flow rate reported outcomes. The authors continuously measured facepiece penetration of a sulfur hexafluoride (SF $_6$) challenge over 3-4 hours of simulated asbestos removal. Work rate was not reported, but the tasks described would likely be classified as moderately heavy work. Neither airflow to the facepiece nor facepiece pressure was

monitored during the tests. Overall reported SWPF values ranged from 2,000 to 20,000 over 20 simulations. The remaining simulation had a SWPF of 400. Our current protocol also incorporates full-facepiece PAPRs to compare their performance to PAPRs with loose-fitting hoods/facepieces, and the design will remove the limitations experienced during this trial.

Seiple and Pappas (2003) tested the 3M Breathe Easy PAPR with a butyl rubber hood in a SWPF study. The challenge agent was 20-40 mg/m³ polydisperse corn oil with a mass median aerodynamic diameter (MMAD) of 0.4-0.6 µm. Laser photometry was used to measure challenge aerosol and penetration on the operating (blower on) PAPR. U.S. Army standard sampling probes were used to collect in-hood samples. Seven standard fit testing exercises plus "sight the rifle," "reach for the floor and ceiling," and "on hands and knees, look left and right" were performed for one minute each by 24 test subjects. All SWPFs were greater than 20,000. Our current protocol also employs a varied set of dynamic exercises to determine the effect of each exercise on particle penetration in the PAPR hood or facepiece, however additionally studies flow rate effects.

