Table 5. Phase II PAPR Models

#	PAPR MODEL	OSHA APF	RIC DESIGN
			tight-fitting full
1	Bullard EVA	1000	facepiece
	2504.00	1000	tight-fitting full
2	MSA OptimAir	1000	facepiece
3	3M Versaflo		
	hood (S-403L (M/L size)	1000	loose-fitting full hood
	hood (S-403S (S/M size)	1000	
4	ILC Dover Sentinel XL		
	S-2019-10 (one-size)	1000	loose-fitting full hood
5	Bullard EVA		
	20TIC hood (one-size)	1000	loose-fitting full hood
6	Maxair Helmet CAPR w/ HE filter (Bio-Medical Devices, Inc.)		
	2261-01ML	25	loose-fitting full hood
	2261-01SM	25	
7	Maxair Helmet CAPR w/ HE filter (Bio-Medical Devices, Inc.)	25	loose-fitting facepiece

[figure not shown]

	3M VersaFlow w/ S133 cuff		
8	facepiece	25	loose-fitting facepiece

Flow Rates

 The two PAPR airflow rates tested in Phase II include: 1) 170 L/min for loose-fitting PAPRs and 115 L/min for tight-fitting PAPRs (based on the current NIOSH minimum certification airflow rates) and 2) 125 L/min for loose-fitting PAPRs and 100 L/min for tight-fitting PAPRs (experimental airflow rates below the NIOSH certification requirement). Flow rates at and below the NIOSH certification minimum, PAPRs will be modified and therefore not NIOSH certified. Modifications to these devices will reduce airflow by one of two ways as determined by the study team: 1) controlling voltage to the PAPR motor, 2) installing a 3-way valve into the blower hose (if equipped) to bleed-off excess flow (Figure 3).

Figure 3. Subject Wearing a PAPR with Fixed Airflow Valve

Simulated Workplace Protection Factor

SWPF testing will take place in both Phase II and Phase III, following the work rate determination in Phase I. Test subjects wearing PAPR will enter the test chamber and complete the exercise regimen (Table 3.) against a corn oil challenge aerosol.

For this test, a TSI Rear Light Scattering Laser Photometer, model 8587A, will be used to measure aerosol concentration inside of the respirators. A TSI model 8520, Dustrak Aerosol Monitor will be used to monitor chamber particle concentrations. Data collected by the laser photometer will be recorded on the NIOSH Dynamic Fit Software. Data will be analyzed using a three-way repeated measures ANOVA with subject number, model, and work rate, and the log transformed SWPF of each test as the dependent variable. The relative importance of each variable to PAPR performance will be determined. The SWPF will be calculated in two steps as follows:

1. Ratio of the Upstream and Downstream Particle Concentrations

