
$$SWPF_{i} = \frac{C_{out}}{C_{in}}$$

 Where: SWPF = simulated workplace protection factor; i = exercise number; $C_{out} = exercise$ upstream particle concentration; $C_{in} = exercise$ downstream particle concentration

2. Overall SWPF for Each PAPR Model

$$Overall SWPF = \frac{n}{\frac{1}{SWPF_1} + \frac{1}{SWPF_2} + \cdots + \frac{1}{SWPF_{n-1}} + \frac{1}{SWPF_n}}$$

Where: $SWPF_n = simulated$ workplace protection factor for a given exercise; n = number of exercises used during an SWPF test.

Test Chamber

The SWPF testing will be conducted inside a 16' x 16' x 10' charged corn oil test chamber in Building 40 of the National Personal Protective Technology Laboratory in Pittsburgh, PA. SWPF test setups are displayed in Figures 4A and 4B.

A 99% stock corn oil (CAS #8001-30-7) with the commercial product names Maise/Maize, Maydol, and/or Mazola oil will be used for test aerosol. It will be aerosolized using an MSP Model 2045 High Output Aerosol Generator capable of maintaining 5 to 100 mg/m³ of corn oil challenge aerosol concentrations for the required test duration. For SWPF testing, the test chamber will be maintained at ~20-40 mg/m³. The output aerosol will be dried with 30% dilution air, followed by neutralization with a Kr-85 charging source before entering into the exposure testing chamber. The aerosol will have a Mass Median Aerodynamic Diameter (MMAD) of 0.4 to 0.6 μ m, with a geometric standard deviation of less than 2.0. This size distribution will be measured once daily using a Scanning Mobility Particle Sizer (SMPS) system. This system is comprised of the TSI model 3080 Electrostatic Classifier, TSI model 3775 Condensation Particle Counter, and 3081 Long Differential Mobility Analyzer (DMA).

The aerosol in the exposure chamber will be mixed using four internal fans positioned in the top four corners of the charged corn oil test chamber, and the chamber conditions will be tracked by a humidity/temperature sensor. Corn oil aerosol particles will be continuously dispersed into the chamber, while an open exhaust port will remove excess air and maintain neutral pressure.

Figure. 4A: Aerosol Chamber Testing System for Loose-Fitting PAPRs

[figure not shown]
[figure not shown]

Figure. 4B: Aerosol Chamber Testing System for Tight-Fitting PAPRs

Subject Monitoring

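### The protocol promises an SWPF for particle sizes 10–1,000 nm, but its measurement plan yields one total-concentration ratio, taken from two instruments with no stated common scale

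*Protocol*

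**What the plan says.** Section 3.3 assigns the instruments. The "TSI Rear Light Scattering Laser Photometer, model 8587A, will be used to measure aerosol concentration inside of the respirators", and for the chamber a "Dustrak Aerosol Monitor will be used to monitor chamber particle concentrations". Section 3.4 repeats this for Phase III: "Laser photometer and Dustrak will be used to measure aerosol concentration inside and outside of the respirator, respectively". Section 5.3 has both instruments recording simultaneously and takes each exercise SWPF as the upstream concentration over the downstream one.

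Size enters in three places:

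- **Section 3.4:** "The SWPF for all particle sizes (10–1,000 nm) inside and outside the respirator will be determined".
- **Section 8.2:** the ratio is formed "for the summation particles across the size range measured, for each exercise". Respirator performance over the measured sizes is then summarised by the geometric mean (GM) and the 5th percentile. Section 8.3 carries this approach into Phase III.
- **Section 3.3, Test Chamber:** the challenge aerosol has an MMAD of 0.4 to 0.6 µm and a GSD below 2.0. "This size distribution will be measured once daily using a Scanning Mobility Particle Sizer (SMPS) system".

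Table 1 and the formula in Section 3.3 define SWPF as outside over inside concentration, with no size term. Table 1 adds that SWPF is expected to reach at least the device's assigned protection factor (APF), 25 or 1,000.

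**The concern.** The Phase III sentence attributes to the result a property that the measurement plan does not show. No sizing inside a respirator is described anywhere, yet the sentence covers both inside and outside. A report that followed the text would claim protection over 10–1,000 nm on the strength of a total-concentration reading dominated by particles of a few hundred nanometres.

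The second issue is scale. The numerator comes from one type of instrument and the denominator from another, and the protocol describes no step that relates their readings. Any difference in response passes straight into the absolute SWPF. That matters where absolute values are used: the GM and 5th percentile of Section 8.2, the APF expectation in Table 1, the exploratory objective of evaluating SWPF as a standard test method (Section 2.3), and the possible changes to the PAPR standard mentioned in Section 3.0.

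**Working it through.** The protocol gives no figure of its own to reproduce here, so there are two supporting checks.

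**1. What the stated aerosol says about the stated bounds**

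Inputs: MMAD 0.4–0.6 µm and GSD below 2.0 (Section 3.3, Test Chamber); bounds 0.01 and 1 µm (Section 3.4). Assumptions: a lognormal mass distribution, and particle density near 1, so that aerodynamic diameter stands for particle diameter. The GSD of 2.0 is the stated ceiling; 1.5 is an assumed narrower case.

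Mass fraction below size d = Φ( ln(d/MMAD) / ln GSD ).

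Above 1 µm:

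| MMAD (µm) | GSD 2.0 | GSD 1.5 |
|---|---|---|
| 0.4 | 1 − Φ(1.32) = 9.3% | 1.2% |
| 0.5 | 1 − Φ(1.00) = 15.9% | 4.4% |
| 0.6 | 1 − Φ(0.74) = 23.1% | 10.4% |

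Below 0.1 µm, at GSD 2.0:

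- MMAD 0.4: Φ(−2.00) = 2.3%
- MMAD 0.5: Φ(−2.32) = 1.0%
- MMAD 0.6: Φ(−2.58) = 0.5%

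Mass below 0.01 µm is negligible. A total-concentration ratio is therefore not confined to sizes under 1,000 nm, and it carries almost no information on 10–100 nm, the lower decade of the promised range.

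**2. What a difference in instrument response does**

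Let k be the Dustrak response divided by the photometer response to the same aerosol. Then observed SWPFᵢ = k × true SWPFᵢ. The overall value n / Σ(1/SWPFᵢ) scales by k. So does the GM, and so does GM/GSD^1.645, because the GSD is unchanged.

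Illustration with an assumed GM of 2,000 and a GSD of 1.5, the low end of the range quoted in Section 3.1. Here 1.5^1.645 ≈ 1.948.

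- k = 1: 5th percentile 2,000 / 1.948 ≈ 1,027
- k = 0.8: about 821
- k = 1.25: about 1,283

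For k between 0.8 and 1.25 (assumed), the reading against an APF of 1,000 can change only if the true 5th percentile lies between 1,000/1.25 = 800 and 1,000/0.8 = 1,250. For an APF of 25 the band is 20 to 31.25.

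On the log scale used for analysis, a constant k adds log k to every value and drops out of every contrast.

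Drift in k between sessions adds variance: new GSD = exp√(ln²GSD + ln(1 + CV²)). With an assumed drift CV of 10%, a GSD of 1.5 becomes 1.52 and 3.5 becomes 3.51. With 30%, they become 1.65 and 3.62.

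Appendix A shows where drift would fall. Both flow rates of a model are tested in one Phase II visit, and both regimens of a model in one Phase III visit. Models are split over visits: 1–2, 3–4, 5–6 and 7–8 in Phase II, in the same order in replicate 2, and 1–4 versus 5–8 in Phase III. Drift therefore bears mainly on the comparison of models and inlet-covering designs.

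**The case against.** A fair reply has several parts, and most of it stands.

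- A reader might infer that SWPF is defined by size and so cannot be computed. The documents do not support that. The definitions are plain concentration ratios, the 10–1,000 nm range appears in one Phase III sentence, and Section 8.2 gives no numerical range. Its wording reads naturally as one aggregate ratio, which the named instruments can deliver.
- That neither device resolves size is inferred from how the protocol describes them. It is not stated, and Figures 4A and 4B, which show the set-up, are not reproduced in the text at hand.
- A reader might also infer that the two-instrument ratio biases the primary comparisons. A constant factor does not. The flow-rate and work-rate contrasts are also made within a visit, so drift between visits largely spares them.
- The protocol's silence on cross-calibration does not show that none is done. Laboratory procedures may cover it.
- Much of the cited PAPR performance lies far above the benchmarks. Section 1.2 reports values above 20,000, 5th percentiles from 150,000 upward, and one study at 2,000 to 20,000 with a single 400. At most of those levels a factor of 0.8 to 1.25 would not alter an APF conclusion.
- The cited studies are weak evidence for requiring a single instrument. One is summarised as "Laser photometry was used to measure challenge aerosol and penetration on the operating (blower on) PAPR", which says that photometry served both sides, not that one unit did.

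What the reply leaves untouched is that the 10–1,000 nm claim does not match the measurement plan, and that the protocol itself requires no common scale for a ratio whose absolute value it intends to use.

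**Conclusion.** The concern holds in a limited form. The size statement in Section 3.4 and the size-range wording in Section 8.2 do not fit the instruments and the once-daily sizing described in Section 3.3. What will be measured is one aggregate concentration ratio for the specified corn-oil aerosol. Under a lognormal distribution with density near 1 and GSD at its ceiling, 9–23% of the mass lies above the upper bound and at most 2.3% lies in the lowest decade of the range.

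The scale issue is secondary. It affects absolute SWPFs, GMs and 5th percentiles in direct proportion to k, and through drift mainly the between-visit comparison of models and inlet coverings. The values of k and its drift are assumptions, since the documents give neither. This point does not put the primary flow-rate and work-rate contrasts in doubt.

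**What to change.** **Text.** In Sections 3.4 and 8.2, state SWPF as the ratio of total aerosol concentrations outside and inside the respirator for the specified challenge aerosol. Remove the 10–1,000 nm bounds and the references to a measured size range, and limit conclusions to that aerosol. If a size claim is wanted, name a size-resolving instrument for both sides instead. The text change costs only a claim that the design does not support.

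**Measurement.** Require a paired reading of the same chamber aerosol on the photometer and the Dustrak, for example at the start and end of each test session. Record the response ratio and use it to put Cout on the photometer's scale.

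This costs a few minutes of instrument time. Two conditions need checking first, because the documents are silent on both:

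- The photometer's range must admit the chamber level of about 20–40 mg/m³.
- Its response must be linear down to in-respirator levels. At an SWPF of 1,000 these are about 20/1,000 = 0.02 to 40/1,000 = 0.04 mg/m³.

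If laboratory procedures already include such a cross-check, a reference to them in Section 3.3 is enough.
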